7.1 Potential Study Risks

The potential risks to participants, their likelihood and seriousness, and strategies to mitigate risks are described below. Participants can choose, as an alternative, to not enroll in this study. Overall, there is minimal risk for serious adverse reactions as a consequence of enrolling in this study. Adverse reactions/AEs will be collected, assessed, and reported as per the study protocol (see section 8: Safety and Adverse Events), federal law, and University of Pennsylvania regulations.

Transdermal Nicotine (TN): Some individuals who use TN patches experience mild skin irritation at the patch site, such as itching, burning, and tingling, which subsides in a few hours. Mild to moderate skin redness, rash, or swelling may also occur. Additionally, participants will be instructed to inform the research staff if they experience an irregular heartbeat or palpitations. Sleep disturbances and vivid dreams may occur, but these sleep-related issues can be resolved by removing the TN patch before going to bed and reapplying a new TN patch in the morning. Other side effects such as, nausea, vomiting, weakness, dizziness, and rapid heartbeat occur rarely and may be related to nicotine overdose. Nicotine overdose is most often caused by continuing to smoke while using the patch. If these reactions occur, and the participant is currently smoking and using the patch (i.e., the participant has relapsed/lapsed but still is wearing the patch), participants will be counseled to reestablish a target quit day and gradually reduce their smoking rate. Participants will not be instructed to discontinue their patches if they have a smoking lapse unless a serious adverse event or experience severe/intolerable side effects. If a participant experiences symptoms of an allergic reaction, such as difficulty breathing or notable rash, they will be instructed to cease use of TN and consult with the research staff and Study Physician immediately.

Other nicotine patch risks can include risks to children and pets if TN patches are not stored or disposed of properly. Unused and used patches have enough nicotine to poison children and pets. Participants will be instructed to keep patches out of the reach of children and pets. Participants will be instructed to fold the sticky ends together when disposing of used patches. Participants will be informed that if a child or pet swallows a nicotine patch, they seek professional help or contact a Poison Control Center immediately.

The overall risk of adverse responses to TN will be minimized by only admitting subjects to the study if they do not have preexisting conditions that significantly increase the risk for adverse responses (e.g., heart disease, uncontrolled high blood pressure, allergy to adhesives, poorly controlled diabetes, etc.) per the product labeling. In addition, no TN will be distributed to a participant without the documented approval (via email) of the Study Physician post Intake. The research staff, in conjunction with the Study Physician and Principal Investigator, will monitor for anticipated side effects of TN per the SEC form and other AE assessment measures (see section 8.2.1: AE Collection Methods) at every in-person visit over the treatment period. Participants will be provided with an information sheet describing the proper use of TN, the possible adverse reactions of TN, and the methods for minimizing the possibility of adverse reactions. Participants will be specifically instructed to contact the study staff or the Study

CONFIDENTIAL

This material is the property of the University of Pennsylvania. Do not disclose or use except as authorized in writing by the study sponsor

Physician if they 1) experience severe or persistent skin reactions (e.g., skin redness, itching, or swelling) caused by the patch that last more than 4 days, or a generalized skin reaction (e.g., hives or rash); 2) notable irregular heartbeat or palpitations (e.g. notable hard or fast beats); 3) persistent nausea, vomiting, dizziness, weakness, or rapid heartbeat (symptoms of nicotine overdose); or 4) symptoms of an allergic reaction such as difficulty breathing or notable rash. Participants should not stop using the patch without discussing their symptoms with the Study Physician and study staff unless they experience severe or intolerable side effects. The Study Physician is knowledgeable of side effects related to TN treatment and is qualified to manage possible side effects. Any severe adverse reactions or significant side effects of TN as identified in section 8.2: Safety and Adverse Events will be medically evaluated by the Study Physician.

Reproductive Risks: Because TN safety for an unborn baby is unknown, participants will be told that they should not become pregnant while in this study. Women in the study should not breast-feed a baby. If a woman is of childbearing potential, she must agree to use an adequate form of contraception or abstain from sexual intercourse for the duration and for at least one month after the end of the trial. If a woman is pregnant or breast-feeding, she should not participate in this study. If she becomes pregnant during the study, she will be asked to notify staff immediately and will be removed from the study. Women will be asked to self-administer a pregnancy test during the Intake Visit (prior to the TN treatment period).

Withdrawal Syndrome: Many individuals who quit smoking exhibit a pattern of symptoms related to withdrawal from tobacco use. These symptoms include: anger, irritability, frustration, anxiousness or nervousness, depressed mood or sadness, cravings for nicotine, difficulty concentrating, appetite change and weight gain, insomnia or other sleep problems, restlessness, impatience, constipation, dizziness, coughing, nightmares, nausea, sore throat, headache, muscular pain, or fatigue. Eliminating the risk for these would not be possible, although in most cases these events are short-lived and have low intensity, lasting for 1-2 weeks. The study personnel will be trained to recognize these symptoms and educate the participants about them (e.g., duration and methods for reducing them).

Food Allergies: Participants will be provided with nutritional shakes and potato chips or milk chocolate and as part of their participation in this research trial. The risk of a participant experiencing an allergic reaction to any of the ingredients in these commercially available food products will be mitigated by prospectively excluding those with the applicable food allergies. In addition, the research staff will reconfirm that the participant doesn't have any of the applicable food allergies prior to distribution of the aforementioned food products at the Baseline Visit.

Psychological Distress: Participants may experience emotional distress during smoking cessation counseling and assessments from discussing feelings and attitudes about smoking or from learning about the risks from smoking. These events happen very rarely and in almost all cases are short-lived and of low intensity, lasting for 1-2 weeks. Study personnel will be alerted to expect this from a small number of subjects and will be trained to make referrals for mental health services as needed. Personnel will be trained to query for adverse emotional reactions during counseling and assessments and will be trained to deal with such reactions and to provide additional referrals if needed.

Urine and Saliva Sample Collection: Participants may experience mild discomfort from providing urine or saliva samples. All samples will be collected by trained member of the research staff.

Email Communications: In this research study participants may prefer to receive appointment reminders via email or submit questions related participation via email. Email is not a secure means of communication. Email messages travel across the Internet passing through multiple

CONFIDENTIAL

This material is the property of the University of Pennsylvania. Do not disclose or use except as authorized in writing by the study sponsor

computers before reaching their final destination. It is not possible to know whether an email a participant sends will be viewed along the way. Additionally, if sent messages are not deleted, an email provider may have an archive of everything that is sent. If someone gets access to an email account (for example, a participant's family member), they could see archived messages. There are many other ways in which emails are not secure—these are only selected examples. To manage this risk the informed consent form will include specific language to educate research participants on the privacy risks involved in email communications. Participants will also be explicitly instructed to only use email communications for routine matters and never for personal or confidential messages or questions.

fMRI: The known MRI-related risks associated with this study are minimal. All sequences and RF coils will be approved by the Center for Magnetic Resonance Imaging and Spectroscopy (CAMRIS) prior to utilization. Because of the strong magnetic field, people with pacemakers, certain metallic implants, or metal in the eye cannot participate in this study. These exclusions will be reviewed carefully with the study staff prior to scanning. Although the Nicoderm® CQ® package insert states that patches should be removed before undergoing any MRI procedures – “for the opaque Nicoderm® CQ® patch only,” we will err on the side of caution and instruct participants in the neuroimaging sub-study to remove their 7mg Nicoderm® CQ® - Clear patch before entering the MRI environment during their Scan 2 Visit only (no patch worn during the pre-treatment scan). Participants will be provided with a loose, sealed 7mg (NicoDerm® CQ® - Clear) patch to reapply after exiting the MRI environment.

The greatest risk with MRI is a metallic object flying through the air toward the magnet and hitting the participant. To reduce this risk we require that all people involved with the study remove all metal from their clothing and all metal objects from their pockets. No metal objects are allowed in the magnet room at any time. In addition, once the participant is in the magnet, the door to the room will be closed so that no one inadvertently walks into the magnetic field. Although there are no known risks of MRI on pregnant women or a fetus, there is a possibility of yet undiscovered pregnancy related risks. Since there is no direct benefit from participating in this protocol for a pregnant woman, women of child bearing potential will be supplied with a simple, CLIA-waived urine pregnancy screen to self-administer at each scan visit, and will be told that pregnant women may not participate in the study. They will then be instructed to administer the pregnancy test independently and will inform study staff if they would like to continue participation after they have administered the pregnancy screen. Participants will be informed that there is no penalty for discontinuing participation at this point in the visit and that they will still receive travel reimbursement for the visit.

There is no known health risk associated with exposure to magnetic fields during an MRI. There are minimal risks from the loud noise associated with the MRI scanner and from the discomfort of lying on a hard surface. Participants will be provided with protective earplugs as necessary and every attempt will be made to ensure comfort with blankets, etc. during the scan.

The levels of energy used to make magnetic resonance measurements are far less than are used in a single X-ray, and many patients have been safely studied using magnetic resonance techniques. However, some people become uncomfortable or claustrophobic while inside the magnet. If participants become uncomfortable, they may withdraw immediately from the fMRI portion of the study. During some of the MRI scans, participants have occasionally reported “tingling” or “twitching” sensations in their arms or legs, especially when their hands are clasped together. To prevent this, all participants will be instructed to keep arms and legs apart.

The imaging component of this study is part of a research protocol, and is not intended to provide a comprehensive clinical fMRI examination of the brain. In the event that a significant

CONFIDENTIAL

This material is the property of the University of Pennsylvania. Do not disclose or use except as authorized in writing by the study sponsor

brain abnormality is observed while processing subject brain images for the research study, the images will be reviewed by the radiologist affiliated with this protocol in conjunction with the Study Physician. There will be no charge to the subject for this examination of their images. A report will be filed in the subject's chart at the Center. The subject will be contacted and Center staff will arrange for the radiologist's report and structural images to be sent to the subject and/or their physician. Subjects will also be offered a consult with the Study Physician and/or radiologist if appropriate. These possible finding(s) may or may not be significant and may lead to anxiety about the subject's condition and to further work-up by the subject's physician.

Risks associated with stool samples (microbiome sub-study only):

Collecting stool may contain germs that spread disease. Participants will be reminded to carefully wash their hands and use the provided gloves to avoid spreading infection. Some people may feel uncomfortable or embarrassed using the stool sample collection kit. There should be no pain while collecting the stool sample. However, if a participant is constipated, straining to pass stool may be painful. We will discuss this risk with the participant during the informed consent presentation to ensure that the individual subject is comfortable with the process.

Risks associated with genetic testing (microbiome sub-study only):

This research includes genetic testing. We will sequence all the genomes present in each stool sample (both human and microbial) via a technique called shotgun metagenomics. Part of the analysis process involves assembling the microbial reads into contigs. We do not assemble contigs from the human data. Even without a name or other identifiers, a participant's genetic information is unique to them. The researchers believe the chance that someone will identify a participant is very small, but the risk may change in the future as people come up with new ways of tracing information. We will not complete genetic testing of inherited traits for research purposes.

Confidentiality and Loss of Privacy: See section 9.7.1 and 9.7.2 for methods in which Confidentiality and Subject Privacy/Protected Health Information will be secured and maintained.

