5.5.3 Dispensing and Reconciliation of Study Drug

The appropriate amount of TN patches will be distributed to eligible participants at week -1 (PQ), week 1 (Mid-Tx.1), and week 4 (Mid-Tx. 3) according to a standardized patch distribution schedule. TN dosage (see section 5.2: Treatment Regimen) will be dependent on the participant’s daily smoking rate reported at the Intake Visit.

Regular study drug reconciliation will be performed to document drug dispensed, drug used, and drug returned. This reconciliation will be logged on both a subject-specific drug reconciliation form maintained in the subject’s study chart, as well as an overall study drug accountability form. Returned or expired TN will be secured and logged into onsite quarantine. UPENN Environmental Health & Radiation Safety (EHRS) will make periodic pick-ups of the quarantined TN for incineration. Records of EHRS pick-ups will be maintained in the study files.

CONFIDENTIAL

This material is the property of the University of Pennsylvania. Do not disclose or use except as authorized in writing by the study sponsor

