documented as **unanticipated (unexpected)** AEs unless they are otherwise outlined in the protocol or consent (i.e. related to withdrawal, assessments, etc.). The reporting period for each assessment will inquire about any event(s) or symptom(s) experienced since the last in-person visit. If a participant reports a symptom or medical event, they will be asked to rate the severity of the event utilizing the following severity scale: 0 (None=No Concerns), 1 (Mild=Issue does not interfere with usual daily activities), 2 (Moderate=Issue does interfere with some activities), and 3 (Severe=No normal activities are possible). Any report on the Open-Ended AE Form will require additional follow up per the AE documentation and internal reporting procedures outlined below in section 8.2.2.

3. **Spontaneous Assessment:** Once enrolled, participants will be instructed to inform the research team about any notable symptom or medical event/concern throughout their participation in the study. A participant may also request the Study Physician be consulted about any reported medical event or concern of any severity at any time throughout their participation. At the Pre-Quit Visit (Week -1), participants will receive an emergency medical card (EMC) with the Study Physician's direct contact information should a medical issue or concern that they believe may be related to the study procedures require immediate attention.

An "AE Note" template will be available to the research staff to collect supporting AE information and will function as the source document. However, research staff may collect AE information on any source document available to them and transfer the relevant information to a formal AE Note at a later time. Any notable AE reported spontaneously will require additional follow up per the AE documentation and internal reporting procedures outlined below in section 8.2.2.

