 - None = No concerns
 - Mild = Side effect or issue does not interfere with usual daily activities
 - Moderate = Side effect or issue interferes with some activities
 - Severe = No normal activities are possible
- Relatedness to the study procedures (PI and/or Study Physician):
 - Unrelated = Definitely not related
 - Unlikely = Doubtfully related
 - Possibly = May be related
 - Probably = Likely related
 - Definitely = Related
- Clinical assessment of subject conducted at time of SAE (if appropriate)
- Results of any laboratory tests and/or diagnostic procedures (if appropriate)
- Autopsy findings (if appropriate)
- Concomitant medications and therapies (excluding treatment of event)
- Relevant Medical History (if appropriate)

Internal Reporting Procedures: All relevant follow-up information outlined above (see AE/SAE documentation) concerning applicable AEs, including all information regarding the occurrence of concurrent smoking and TN (if applicable) and previously reported event(s) and/or side effects, will be reported to the Study Coordinator (or other senior personnel), Principal Investigator, and

CONFIDENTIAL

This material is the property of the University of Pennsylvania. Do not disclose or use except as authorized in writing by the study sponsor

Study Physician to determine a course of action (e.g. continue to monitor, reduce medication dose, stop medication), relatedness (causality) to the study, and expectedness (if not already established). This consult will be documented via email. The clinical course of each event will be followed until resolution, stabilization, or until it has been determined that the study treatment or participation is not (or unlikely) to be the cause.

SAEs that are still ongoing at the end of the study period must be followed up to determine the final outcome unless it has been determined that the study treatment or participation is not the cause. Any SAE that occurs after the study period and is considered to be possibly related to the study treatment or study participation should be recorded and reported immediately per this protocol.

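### Section 7.1 gives two different first actions for an allergic or generalized rash that is neither severe nor intolerable: stop the patch at once, or keep it on until discussed

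*Combined protocol and SAP*

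**What the plan says.** Both rules stand in section 7.1 (Potential Study Risks), in the entry on transdermal nicotine.

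The first paragraph of that entry ends with the rule for allergic symptoms, with difficulty breathing and notable rash as its examples. Such participants are handled as follows: "they will be instructed to cease use of TN and consult with the research staff and Study Physician immediately". The rule carries no severity condition. The sentence just before it, on participants who lapse to smoking, does carry one: they are not told to give up the patch "unless a serious adverse event or experience severe/intolerable side effects".

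The later paragraph on minimizing risk lists four reasons to contact the study staff or the Study Physician. The last is "4) symptoms of an allergic reaction such as difficulty breathing or notable rash". The first reason includes a generalized skin reaction, with hives or rash as examples. The next sentence, which concerns side effects at large, reads in part: "Participants should not stop using the patch without discussing their symptoms with the Study Physician and study staff unless they experience severe or intolerable". It makes no exception for item 4 or for the generalized reaction in item 1.

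The same paragraph mentions what participants are handed: "Participants will be provided with an information sheet describing the proper use of TN". That sheet is not among the documents.

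**The concern.** What to do first with a suspected allergic reaction to a study drug should have one answer. Participants wear the patch at home, and from week 2 to week 8 the scheduled visits are two weeks apart (section 3.1), so the instruction has to work without staff in the room. Someone who follows the allergy rule takes the patch off and calls. Someone who follows the later paragraph with the same rash calls and keeps the patch on until the symptoms have been discussed. Staff are trained on the protocol (section 10.2), so if its text points two ways, so may the advice they give.

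What is at stake is continued exposure to the patch between noticing the rash and reaching someone.

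**Working it through.** There is no figure to reproduce. The check sets the two rules side by side, case by case.

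| Presentation | Allergy rule (first paragraph) | Contact list and the sentence after it (later paragraph) | Same first action? |
|---|---|---|---|
| Allergic symptoms, severe or intolerable | Stop and consult | Contact; stopping allowed | Yes |
| Allergic notable rash, neither severe nor intolerable | Stop and consult | Contact (item 4); do not stop before discussion | No |
| Generalized hives or rash, neither severe nor intolerable, seen as allergic | Stop and consult | Contact (item 1); do not stop before discussion | No |
| Other listed symptoms, not severe or intolerable | Silent | Contact; do not stop before discussion | No conflict |

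**Is the conflict zone empty?** It would be if every allergic rash counted as severe or intolerable. The protocol does not say so. The side-effect scale (sections 6.5.2, 8.2.1 and 8.2.2) reserves its top grade for events that leave no normal activity possible, and section 7.1 itself expects mild to moderate rash on the patch. A rash can be notable without reaching that grade. Section 7.1 does not cite the scale, however, and neither notable nor intolerable is defined, so this is supporting evidence only.

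**How many contact reasons are involved?** Two of four. Item 4 repeats the allergy trigger almost word for word. Item 1 overlaps with it, because a generalized rash or hives can be an allergic sign. The do-not-stop sentence contains no exception for either, and the allergy rule contains no severity threshold.

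**Does another section settle the order?**

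- Section 6.5.1 says only that TN is monitored, adjusted or discontinued as needed when side effects are notable.
- Section 8.2.1 requires follow-up of even a mild rash reported on the checklist.
- Section 8.2.2 sends reports to senior staff, the investigator and the Study Physician "to determine a course of action (e.g. continue to monitor, reduce medication dose, stop medication".

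All of these operate once staff know of the event. None says what the participant does before that.

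**The case against.** The strongest reply is that the specific rule governs the general one. The allergy sentence addresses one kind of event, the do-not-stop sentence addresses side effects at large, and both sit in the same entry. Read that way there is one answer: stop. This is plausible, and it is why confidence is moderate. It does not dispose of the point, because the later paragraph is not remote or purely general. It names the allergic symptoms and gives the do-not-stop rule in the very next sentence, and no priority is stated.

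A second reply is that the rules apply in sequence: the participant calls, and staff then give the instruction to stop. But the allergy rule tells the participant to cease TN and to consult the research staff immediately. That fits poorly with someone already speaking to those staff.

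A third is that item 4, which pairs notable rash with difficulty breathing, is meant for serious reactions that already meet the exception. The documents neither confirm nor exclude this. Difficulty breathing would plausibly qualify as severe. A notable rash alone need not.

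The point about safeguards stands. Allergy to adhesive tape is an exclusion (section 4.6). Participants receive an emergency card with the Study Physician's direct contact details at the Pre-Quit Visit (section 8.2.1), the visit at which patches are first handed out (section 5.5.3).

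A reader might infer something stronger: that participants were actually given contradictory instructions, or that anyone with an allergic reaction is told to keep the patch on. The documents support neither. The information sheet is not available, so what participants are told is unknown, and severe or intolerable reactions may be met by stopping under both rules.

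**Conclusion.** The inconsistency is real and narrow. For an allergic or generalized rash below severe or intolerable, section 7.1 gives two first actions, and the text does not say which prevails. Severity is minor and confidence moderate.

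The effect is confined to whether the patch stays on until staff are reached. No endpoint, analysis or eligibility rule depends on it. The documents give no rate of allergic reactions to TN, so the number of participants affected cannot be estimated.

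The conclusion rests on two assumptions: that a notable or generalized rash can fall short of severe or intolerable, and that a generalized rash or hives may be an allergic sign. It is a finding about the protocol text, not about what happened to any participant.

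**What to change.** Split the do-not-stop sentence in section 7.1 into two parts:

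1. A participant with allergic symptoms (item 4), including a generalized skin reaction such as hives or rash (item 1), takes the patch off and contacts the study staff and the Study Physician immediately.
2. For all other symptoms, the present rule stays: discuss before stopping, unless side effects are severe or intolerable.

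Exempting item 4 alone would not be enough. A participant with generalized hives or rash would still have to decide whether it counted as item 1 (do not stop) or item 4 (stop).

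Then check that the TN information sheet says the same.

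The cost is one reworded sentence and one document check, with no change to design or analysis. The downside is that a few participants may briefly remove a patch for a benign rash before staff advise them. Section 6.5.1 already lets participants who discontinue TN for a medical event stay in the study.
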